5.2 Secondary Efficacy Evaluation Results

The secondary outcomes of this clinical trial include the time to sputum *Mycobacterium TB* (MTB) culture conversion to negative (liquid and solid culture media), the proportion of sputum MTB culture conversion to negative at two months of treatment (liquid and solid culture media), the proportion of sputum MTB culture conversion to negative at six months of treatment (liquid and solid culture media), the proportion of treatment success at the end of treatment, the proportion of relapse after treatment success (investigational arm), and the proportion of death and time-to-death. Additionally, the primary outcome between treatment groups according to resistance to pyrazinamide is performed.

5.2.1 Time to sputum culture conversion after the initiation of treatment (Liquid and Solid Culture Media)

To test whether the time to sputum culture conversion after the initiation of treatment of the control arm and investigational arm (liquid and solid culture media) are different statistically, the median time is estimated in each group using the Kaplan-Meier method, and the difference of the distribution of time to culture conversion of the two arms is compared using the Log-rank test (Table 16).

Table 16. Time to sputum culture conversion after the initiation of treatment (Liquid and Solid Culture Media)

[figure not shown]
		Investigational Arm	Control Arm	p-value ¹⁾
mITT analysis group, n		xx	xx	
Solid media	median time [95% CI]	xx[xx.xx-xx.xx]	xx[xx.xx-xx.xx]	0.xxxx
Liquid media	median time [95% CI]	xx[xx.xx-xx.xx]	xx[xx.xx-xx.xx]	
PP analysis group, n				
Solid media	median time (95% CI)	xx[xx.xx-xx.xx]	xx[xx.xx-xx.xx]	0.xxxx

Liquid media	median time (95% CI)	xx[xx.xx-xx.xx]	xx[xx.xx-xx.xx]	
Sub-group analysis		xx	xx	
1-1. Sputum smear positive ²⁾		xx	xx	
mITT analysis group, n		xx	xx	
Solid media	median time [95% CI]	xx[xx.xx-xx.xx]	xx[xx.xx-xx.xx]	0.xxxx
Liquid media	median time [95% CI]	xx[xx.xx-xx.xx]	xx[xx.xx-xx.xx]	
PP analysis group, n				
Solid media	median time (95% CI)	xx[xx.xx-xx.xx]	xx[xx.xx-xx.xx]	0.xxxx
Liquid media	median time (95% CI)	xx[xx.xx-xx.xx]	xx[xx.xx-xx.xx]	
1-2. Sputum smear negative ³⁾		xx	xx	
mITT analysis group, n		xx	xx	
Solid media	median time [95% CI]	xx[xx.xx-xx.xx]	xx[xx.xx-xx.xx]	0.xxxx
Liquid media	median time [95% CI]	xx[xx.xx-xx.xx]	xx[xx.xx-xx.xx]	
PP analysis group, n				
Solid media	median time (95% CI)	xx[xx.xx-xx.xx]	xx[xx.xx-xx.xx]	0.xxxx
Liquid media	median time (95% CI)	xx[xx.xx-xx.xx]	xx[xx.xx-xx.xx]	

¹⁾ P-value for the comparison test of the time to negative between Investigational arm and Control arm. The test assumes that the negative distribution difference between Investigational and Control arm is the same at all time points.

²⁾ Sputum smear positive at screening visit (visit1)

³⁾ Sputum smear negative at screening visit (visit1)

[figure not shown]

Figure 2. Time to Sputum Culture Conversion after Initiation of treatment (Liquid and Solid Culture media)

5.2.2 Sputum culture conversion proportion at two months of treatment (Liquid and Solid Culture Media)

- To compare the proportion of sputum MTB culture conversion to negative between the investigational arm and control arm at two months of treatment, the frequency and proportion of each arm are summarized, and the Chi-square test or Fisher's exact test is performed (Table 17).

Table 17. Sputum culture conversion proportions at two months of treatment

		Investigational Arm	Control Arm	p-value ¹⁾
mITT analysis group, xx persons (Investigational arm: xx persons, Control arm: xx persons)				
Solid media	n (%)	xx (xx.xx)	xx (xx.xx)	0.xxxx †† or **
Liquid media	n (%)	xx (xx.xx)	xx (xx.xx)	0.xxxx †† or **
PP analysis group, xx persons (Investigational arm: xx persons, Control arm: xx persons)				
Solid media	n (%)	xx (xx.xx)	xx (xx.xx)	0.xxxx †† or **
Liquid media	n (%)	xx (xx.xx)	xx (xx.xx)	0.xxxx †† or **
Sub-group analysis				
1-1. Sputum smear positive ²⁾				
mITT analysis group, xx persons (Investigational arm: xx persons, Control arm: xx persons)				
Solid media	n (%)	xx (xx.xx)	xx (xx.xx)	0.xxxx †† or **
Liquid media	n (%)	xx (xx.xx)	xx (xx.xx)	0.xxxx †† or **
PP analysis group, xx persons (Investigational arm: xx persons, Control arm: xx persons)				
Solid media	n (%)	xx (xx.xx)	xx (xx.xx)	0.xxxx †† or **
Liquid media	n (%)	xx (xx.xx)	xx (xx.xx)	0.xxxx †† or **
1-2. Sputum smear negative ³⁾				
mITT analysis group, xx persons (Investigational arm: xx persons, Control arm: xx persons)				
Solid media	n (%)	xx (xx.xx)	xx (xx.xx)	0.xxxx †† or **
Liquid media	n (%)	xx (xx.xx)	xx (xx.xx)	0.xxxx †† or **
PP analysis group, xx persons (Investigational arm: xx persons, Control arm: xx persons)				
Solid media	n (%)	xx (xx.xx)	xx (xx.xx)	0.xxxx †† or **
Liquid media	n (%)	xx (xx.xx)	xx (xx.xx)	0.xxxx †† or **

†† p-value by the Chi-square test ** p-value by the Fisher's exact test

¹⁾ p-value of the comparison test of the negative conversion rate between the Investigational arm and Control arm

²⁾ Sputum smear positive at screening visit (visit1)

³⁾ Sputum smear negative at screening visit (visit1)

5.2.3 Sputum culture conversion proportion at six months of treatment (Liquid and Solid Culture Media)

To compare the proportion of sputum MTB culture conversion to negative between the investigational arm and control arm at six months of treatment, the frequency and proportion of each arm are summarized, and the chi-square test or Fisher's exact test is performed (Table 18).

Table 18. Sputum culture conversion proportion at six months of treatment

		Investigational arm	Control arm	p-value ¹⁾
mITT analysis group		xx	xx	
Solid media	n (%)	xx (xx.xx)	xx (xx.xx)	0.xxxx †† or **
Liquid media	n (%)	xx (xx.xx)	xx (xx.xx)	0.xxxx †† or **
PP analysis group		xx	xx	
Solid media	n (%)	xx (xx.xx)	xx (xx.xx)	0.xxxx †† or **
Liquid media	n (%)	xx (xx.xx)	xx (xx.xx)	0.xxxx †† or **
Sub-group analysis		xx	xx	
1-1. Sputum smear positive ²⁾		xx	xx	
mITT analysis group		xx	xx	
Solid media	n (%)	xx (xx.xx)	xx (xx.xx)	0.xxxx †† or **
Liquid media	n (%)	xx (xx.xx)	xx (xx.xx)	0.xxxx †† or **
PP analysis group		xx	xx	
Solid media	n (%)	xx (xx.xx)	xx (xx.xx)	0.xxxx †† or **
Liquid media	n (%)	xx (xx.xx)	xx (xx.xx)	0.xxxx †† or **

1-2. Sputum smear negative ³⁾		xx	xx	
mITT analysis group		xx	xx	
Solid media	n (%)	xx (xx.xx)	xx (xx.xx)	0xxxx †† or **
Liquid media	n (%)	xx (xx.xx)	xx (xx.xx)	0xxxx †† or **
PP analysis group		xx	xx	
Solid media	n (%)	xx (xx.xx)	xx (xx.xx)	0xxxx †† or **
Liquid media	n (%)	xx (xx.xx)	xx (xx.xx)	0xxxx †† or **

†† p-value by the Chi-square ^{test} ** p-value by the Fisher's exact test

¹⁾ p-value of the comparison test of the negative rate between the Investigational and Control arms

²⁾ Sputum smear positive at screening visit (visit1)

³⁾ Sputum smear negative at screening visit (visit1)

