5.4. Inclusion Criteria

- 1) Men and women age ≥ 19 and ≤ 85
- 2) Confirmed pulmonary MDR-TB by phenotypic or genotypic drug susceptibility tests or RR-TB by genotypic tests such as Xpert® MTB/RIF assay regardless of being positive for sputum acid-fast bacilli smear
- 3) Use of current anti-TB regimen with second-line drugs for ≤ 14 days at the time of enrollment

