6.1. Culture Conversion to Negative

- i. Culture is considered to have converted to negative when two consecutive cultures, taken at least 4 weeks apart, are found to be negative.
- ii. When a subject cannot produce sputum after the first culture negative sputum, that is also defined as culture conversion.
- iii. Encourage to expectorate sputum as much as possible (including induced sputum), but if the subject cannot produce sputum, it will not be deemed as protocol violation.

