8.3. Baseline Visit and Beginning of Treatment

- AFB smear microscopy, and MTB culture on liquid and solid media of sputum or bronchoscopic specimen will be performed.
- CXR, ECG, complete blood count, electrolytes, chemistry (albumin, total bilirubin, alkaline phosphatase, AST, ALT, Creatinine), anti-HIV antibody and HBsAg will be performed.
- Ishihara Test for Color-blindness will be performed to check baseline abnormalities of color blindness.

* Tests could be skipped in case of having available results or tests were performed recently within four weeks (In case of ECG, within a week).

* Study drugs can be administered before the obtaining of anti-HIV Ab, HBsAg, and alkaline phosphatase results since eligibility is not determined by these results.

* Administration of anti-TB regimen can begin at baseline visit since drug-resistant TB must be treated immediately.

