3.1 General Principle of Result Analysis

Data obtained from subjects through clinical trial will be analyzed by mITT (modified Intention-To-Treatment) analysis and PP (Per-Protocol) analysis. Efficacy evaluation will be based on a mITT (modified Intention-To-Treatment) and additional analysis on PP (Per-Protocol) group. Safety analysis will be performed on mITT, PP and the safety group (study drug administration group).

Subject Group	Definition
mITT	
- The mITT group includes participants who are randomized after satisfying eligibility criteria and receive study drugs at least one time. The subjects are not confirmed to be additionally resistant to fluoroquinolone, mono-resistant to rifampicin, or susceptible to rifampicin.

PP	
The PP (Per-Protocol) group includes participants that satisfy the following among the mITT group.
 
When completing over 80% of the planned treatment
 
: For control arm, 64 weeks or longer treatment; For investigational arm, 32 weeks or longer treatment in the 9-month treatment group and 42 weeks or longer treatment in the 12-month treatment group

Safety	
Participants who completed the study per protocol during the clinical trial period
 
: More than 80% of the planned period before treatment is completed, the following cases are considered protocol violation and excluded from the analysis group
 
① withdrawal or death.② The sputum test before culture conversion was not conducted③ Administration of study drug in the control arm 
The Safety analysis group includes participants who have taken study drugs at least one time.
 
: Evaluation based on the administration of study drug (delamanid or linezolid)

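### The culture-conversion tables use all mITT and PP participants, although neither eligibility nor the definition of conversion requires an earlier positive culture

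*Combined protocol and SAP*

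**What the plan says.** **Entry.** Protocol 5.4 accepts "RR-TB by genotypic tests such as Xpert® MTB/RIF assay regardless of being positive for sputum acid-fast bacilli smear". It also allows "Use of current anti-TB regimen with second-line drugs for ≤ 14 days at the time of enrollment". Neither 5.4 nor 5.5 asks for a positive culture. At the baseline visit (Protocol 8.3), "MTB culture on liquid and solid media of sputum or bronchoscopic specimen will be performed", so the sputum itself need not have grown MTB.

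**Analysis set.** SAP 3.1: "The mITT group includes participants who are randomized after satisfying eligibility criteria and receive study drugs at least one time". It then removes only participants confirmed to have fluoroquinolone resistance, rifampicin mono-resistance or rifampicin susceptibility. There is no culture condition.

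**Definition.** Protocol 6.1: "Culture is considered to have converted to negative when two consecutive cultures, taken at least 4 weeks apart, are found to be negative". One negative result followed by inability to produce sputum also qualifies. Protocol 6.2 dates conversion at the first negative. A footnote to SAP 3.6.2 adds that a contaminated culture after a first negative counts too.

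**Tables.** The header of Table 17 is "mITT analysis group, xx persons (Investigational arm: xx persons, Control arm: xx persons", and that of Table 16 is "mITT analysis group, n". Table 18 follows the same pattern, and PP rows repeat it. The only subgroups are by smear. Table 8 (SAP 4.3.6) has rows for negative, contaminated and not-done cultures on each medium at screening and at baseline. The plan therefore foresees such participants but gives no rule for them in the conversion analyses.

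**The concern.** Conversion is an event that can happen only to someone who was positive. A participant with no positive culture on a medium is not at risk of it on that medium, yet the plan places that participant in the denominator. Under the literal definition, the participant can also enter the numerator at once. A week-0 negative confirmed at week 4 is back-dated to week 0.

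At stake are the estimates in Tables 16 to 18: the median times, the two- and six-month proportions and the comparisons between arms. The problem is likely to be greatest in the smear-negative subgroup. Results on solid and liquid media would also fail to describe the participants at risk on each medium. The SAP says it exists to prevent unplanned analysis. In an open-label trial, it is better not to leave this rule until the data are in hand.

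**Working it through.** **The plan's own figures.** The documents give no sample size or power for the conversion outcomes. The only sizing is for the primary outcome: 48 per arm, then 48/(0.50 × 0.95) = 101.05, rounded up to 102 per arm. This is reproduced but does not bear on the point. Half of 102, i.e. 51 per arm, serves below as an illustrative mITT size.

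**Inputs that have to be assumed.** The share f of mITT participants without a positive baseline culture is taken as 10, 20 or 30%. Two-month conversion among baseline-positive participants is taken as p = 80% (investigational) and 60% (control). Neither is in the documents.

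**Proportions, f equal in both arms.** If every baseline-negative participant counts as converted, the reported rate is f + (1−f)p and the reported difference is (1−f)(p_T − p_C). If they all count as non-converters, the rate is (1−f)p and the difference is the same. Power is for a two-sided 5% test (normal approximation, pooled variance under the null). It compares all mITT, counted as converters, with the baseline-positive subset of 51(1−f) per arm.

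| f | Counted as converters | Counted as non-converters | Difference | Power, all mITT | Power, restricted |
|---|---|---|---|---|---|
| 10% | 82 vs 64% | 72 vs 54% | 18 points | 53.6% | 55.3% |
| 20% | 84 vs 68% | 64 vs 48% | 16 points | 47.2% | 50.5% |
| 30% | 86 vs 72% | 56 vs 42% | 14 points | 41.0% | 45.3% |

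The shrinkage factor does not depend on p: with 70% vs 50% the differences are again 18, 16 and 14 points. With 95% vs 85% they are 9, 8 and 7 points in place of 10, and restriction changes power by less than 2 points.

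**Medians.** Assume exponential conversion with medians m of 6 and 9 weeks among baseline-positive participants, and baseline-negatives converting at time zero. Solving (1−f) × 0.5^(t/m) = 0.5 gives t = m[1 + ln(1−f)/ln 2].

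| f | Medians (weeks) | Gap (weeks) |
|---|---|---|
| 0 | 6.00, 9.00 | 3.00 |
| 10% | 5.09, 7.63 | 2.54 |
| 20% | 4.07, 6.10 | 2.03 |
| 30% | 2.91, 4.37 | 1.46 |

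**Unequal f.** Suppose true conversion is 60% in both arms, with f = 25% in one and 15% in the other. The reported rates are 0.25 + 0.75 × 0.60 = 70% and 0.15 + 0.85 × 0.60 = 66%, a 4-point difference with no true effect behind it.

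**The case against.** The strongest reply is that no sentence says baseline-negative participants are converters. A culture that has converted implies one that was positive, and reversion is defined relative to conversion. The denominator is inferred from table headers with placeholders. This stands as far as it goes: the text is silent rather than explicit. But if a prior positive is implied, baseline-negatives can never be counted and the all-mITT denominator is still wrong. Either reading needs a rule.

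Other limits also stand:

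- The formula takes every baseline-negative participant as converted by two months. Two negatives must be four weeks apart unless sputum ceases or a culture is contaminated. Some of these participants may later grow MTB, die or withdraw. The inflation shown is therefore an upper bound for each f. The difference shrinks by less than the full factor if baseline-negatives who later grow MTB also respond to the regimen.
- A reader might infer that the bias always runs toward no difference. That requires equal f, and randomization is stratified by cavitation and diabetes, not by culture or smear (Protocol 8.2).
- The one comparison of conversion rates in the documents (Protocol 3.1, two fluoroquinolones, three months) gives 88.3% and 90.5%. It is no forecast for this trial, but at f = 20% its 2.2-point gap would become 0.8 × 2.2 = 1.8 points, a small change.
- The smear-positive subgroup is a partial safeguard, and Table 8 already reports baseline cultures by arm. Smear is not culture, however, and Table 8 does not change who enters Tables 16 to 18.

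**Conclusion.** The point holds as a gap in the definition of the conversion analysis set. Followed literally, the plan puts participants who are not at risk into the denominator on each medium and can count them as converters near time zero. With equal shares the arm difference shrinks by up to (1−f); with unequal shares it can move either way. The figures of 18, 16 and 14 points rest wholly on assumed f and assumed rates.

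Two stronger readings are not supported. One is that the trial's main conclusion is at risk: the 24-month success comparison does not use these tables, and SAP 3.6.2 treats the secondary outcomes as exploratory. The other is that the plan forfeits important power: in the 80% vs 60% example the restricted set gains about 2 to 4 points, and near the ceiling almost nothing. The harm is to the estimates and their interpretation. The change should be made, but the issue is not critical.

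**What to change.** In SAP 3.6.2 and Tables 16 to 18, define the main conversion set separately for solid and liquid media as the mITT (and PP) participants with at least one positive MTB culture on that medium at screening or baseline. State that participants whose screening and baseline cultures on that medium are all negative, contaminated or not done are left out of this set, and report their numbers per arm by reason. Keep the all-mITT result as a sensitivity analysis, with an explicit rule for how these participants are coded in it.

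The cost is SAP wording and table shells, since screening and baseline cultures on both media are already scheduled. The downside is smaller denominators that differ by medium. Some participants who were truly at risk but had contaminated or missing cultures will be left out, which is why the counts by reason and the sensitivity analysis are needed.

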Regimen consists of only oral medication using delamanid, linezolid, levofloxacin, and pyrazinamide, for nine or twelve months.

- Treatment duration

- A total of 9 months (40 weeks) when sputum culture conversion to negative occurs within three months of treatment
- A total of 12 months (52 weeks) when sputum culture conversion to negative occurs between 3 and 6 months of treatment

- Combination of treatment regimen

- Delamanid, 200mg/day (100mg bid)
 - Use for the entire treatment period unless it must be stopped for reasons such as adverse events.
- Linezolid
 - 600mg/day during the first two months
 - 300mg/day afterwards until the end of treatment

Confidential

MDR-END v14.0, 20Mar2020

- If linezolid re-administration is required after temporary discontinuation due to adverse events, the dose reduction to 300mg is allowed even within two months of treatment.
- Levofloxacin
 - $\leq 50\text{kg}$, 750mg/day
 - $>50\text{kg}$, 1000mg/day
 - Can be reduced or substituted with moxifloxacin due to reasons such as adverse events, and at this time, QT prolongation should be observed closely. Also, this substitution will not be considered as a drug change since both are fluoroquinolones of similar potency.
 - Once a day
- Pyrazinamide
 - $<50\text{kg}$, 1000mg/day
 - 50-70kg, 1500mg/day
 - $>70\text{kg}$, 2000mg/day
 - Can be reduced due to adverse event. Even if pyrazinamide resistance is discovered on the phenotypic drugs susceptibility testing after commencing treatment, it can be continued (20).
 - Once or divide in two or three

Since the definition of treatment outcomes follows the 2014 WHO Guidelines (20), as described in the ‘Research Protocol 6. Definition’, the change of a drug is allowed according to medical judgments, such as adverse drug reactions. However, the change of two or more drugs is considered ‘treatment failed’ and the participants will be withdrawn from the study.

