6.4. Treatment Outcome Definitions

Definitions of treatment outcomes refer to 2014 WHO Guidelines (20). For investigational group, 6 months will be considered as intensive phase.

<Definitions of treatment outcomes for drug-resistant patients>

TREATMENT OUTCOME	DEFINITION
Cured	Treatment completed as recommended by the national policy without evidence of failure AND three or more consecutive cultures taken at least 30 days apart are negative after the intensive phase. ^a
Treatment completed	Treatment completed as recommended by the national policy without evidence of failure BUT no record that three or more consecutive cultures taken at least 30 days apart are negative after the intensive phase. ^a
Treatment failed	Treatment terminated or need for permanent regimen change of at least two anti-TB drugs because of: 
•Lack of conversion^b by the end of the intensive phase^a; or•Bacteriological reversion^b in the continuation phase after conversion^b to negative; or•Evidence of additional acquired resistance to fluoroquinolones or second-line injectable drugs; or•Adverse drug reactions.

Died	A patient who dies for any reason during the course of treatment.
Lost to follow-up	A patient whose treatment was interrupted for two consecutive months or more.
Not evaluated	A patient for whom no treatment outcome is assigned. (This includes cases “transferred out” to another treatment unit and whose treatment outcome is unknown).
Treatment success	The sum of Cured and Treatment completed.

^a For Treatment failed, lack of conversion by the end of the intensive phase[†] implies that the patient does not convert within the maximum duration of the intensive phase[†] applied by the programme. If no maximum duration is defined, an 8-month cut-off is proposed. For regimens without a clear distinction between intensive and continuation phases, a cut-off eight months after the start of treatment is suggested to determine when the criteria for Cured, Treatment completed and Treatment failed start to apply. (†For investigational group, 6 months will be considered as intensive phase.)

^b The terms “conversion” and “reversion” of culture as used here are defined as follows :

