4.1 Subject Participation Status in Clinical Trial

The subject distribution can be summarized as follows as the result of the clinical trial (Figure 1 and Table 1).

[figure not shown]

Figure 1. Subject Enrollment Distribution

Table 1. Clinical Trial Results

	Investigational Arm	Control Arm
Enrollment, n	xx	xx
Non administration of study drug	xx	xx
No randomization due to screening failure	xx	xx
Violation of inclusion/exclusion criteria	xx	xx
Violation of the inclusion criterion 1	xx	xx
Violation of the inclusion criterion 2	xx	xx
Violation of the inclusion criterion 3	xx	xx
Violation of the exclusion criterion 1	xx	xx
Violation of the exclusion criterion 2	xx	xx
Violation of the exclusion criterion 3	xx	xx
Violation of the exclusion criterion 4	xx	xx
Violation of the exclusion criterion 5	xx	xx
Violation of the exclusion criterion 6	xx	xx
Violation of the exclusion criterion 7	xx	xx
Violation of the exclusion criterion 8	xx	xx
Fluoroquinolone resistance confirmed during the study	xx	xx
Rifampicin mono-resistance confirmed during the study	xx	xx
Rifampicin susceptibility confirmed during the study	xx	xx
mITT analysis group, n	xx	xx
Treatment of less than 80% throughout the planned period	xx	xx
Withdrawal or death before treatment completion (less than 80% of the planned period)	xx	xx
Investigator's judgment that participating in the study is not beneficial to the subject	xx	xx

Withdrawal of consent	xx	xx
Treatment failure	xx	xx
Pregnancy	xx	xx
Death	xx	xx
Non-execution of sputum testing before culture conversion to negative	xx	xx
Administration of study drug in the control arm	xx	xx
PP analysis group, n	xx	xx

※ Safety analysis (per the administration of study drugs)

	Investigational Arm	Control Arm	Total
Number of enrollments, n	xx	xx	xx
Non-administration of study drug	xx	xx	xx
Safety analysis (per the administration of study drugs), n	xx	xx	xx
Administration of Delamanid or linezolid	xx	xx	xx
No administration of Delamanid or linezolid	xx	xx	xx

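### In SAP Table 18 the per-protocol test of six-month culture conversion selects the investigational arm on the outcome being tested, so on the medium that sets treatment duration it can never favour control

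*Combined protocol and SAP*

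**What the plan says.** SAP 5.2.3 states the purpose of the six-month analysis as "To compare the proportion of sputum MTB culture conversion to negative between the investigational arm and control arm at six months of treatment", with a chi-square or Fisher's exact test. Table 18 provides a p-value for solid and for liquid media in the mITT set and again in the PP set, overall and by smear status. Tables 16 (time to conversion) and 17 (conversion at two months) have the same PP blocks.

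Membership of PP is set in SAP 3.1 by at least 80% of planned treatment:

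- Investigational: "For investigational arm, 32 weeks or longer treatment in the 9-month treatment group and 42 weeks or longer treatment in the 12-month treatment group". No threshold is given for anyone outside these two groups.
- Control: "For control arm, 64 weeks or longer treatment".

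Protocol 5.1.2 assigns the investigational duration by conversion time: "A total of 9 months (40 weeks) when sputum culture conversion to negative occurs within three months of treatment", and "A total of 12 months (52 weeks) when sputum culture conversion to negative occurs between 3 and 6 months of treatment". No duration is given for later or absent conversion.

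On failure, Protocol 6.4 says "For investigational group, 6 months will be considered as intensive phase" and lists lack of conversion by the end of that phase among the grounds for treatment failure. Protocol 8.7 makes treatment failure a reason for withdrawal. SAP Table 1 removes from PP those with "Withdrawal or death before treatment completion (less than 80% of the planned period"), and treatment failure is one of the reasons itemised beneath it. For control, Protocol 5.1.2 recommends an intensive phase of at least 8 months, and note a in Protocol 6.4 adds: "If no maximum duration is defined, an 8-month cut-off is proposed".

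**The concern.** Entry to the investigational PP set presupposes the event that Table 18 counts. Entry to the control PP set does not presuppose it by the same date. The PP test therefore compares an arm selected on its own outcome with an arm that is selected differently, and a gap can appear when the regimens convert sputum equally fast.

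In an open-label non-inferiority trial, readers look to PP for confirmation of mITT. Earlier conversion is also one of the benefits claimed for the new regimen (expected effects, in the protocol summary), so a PP result of 100% against something lower would be read as evidence of faster bacterial clearance. Neither document restricts the conversion tests to mITT or mentions the selection.

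**Working it through.** **1. The plan's own thresholds.** Planned durations are 40 and 52 weeks (Protocol 5.1.2) and 80 weeks for control (start of the end-of-treatment column, Protocol 7.1).

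- 0.80 × 40 = 32.0
- 0.80 × 52 = 41.6, rounded up to 42
- 0.80 × 80 = 64.0

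All three reproduce. Month 6 is about week 26, short of both 32 and 42, so an investigational participant who leaves as a non-converter at month 6 cannot have qualified.

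**2. The same course in each arm.** Take a participant whose first negative culture falls in month 7.

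- Investigational: belongs to neither duration group, has a listed ground for failure at month 6, and is not in PP.
- Control: still within the recommended intensive phase, can go on to 64 weeks, and is in PP as a non-converter at month 6.

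**3. What this does to Table 18.** Let x be the number converted by month 6 in each arm (equal by assumption) and k the number of controls converting in months 6 to 8. Assume that controls unconverted at month 8 fail and leave PP, and that nobody leaves for other reasons. Then the investigational PP proportion is x/x = 100% and the control PP proportion is x/(x + k). With the 48 evaluable per arm of SAP 2.3.1:

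| x | k | mITT, both arms | PP investigational v control | Fisher p | Uncorrected chi-square p |
|---|---|---|---|---|---|
| 43 | 0 | 43/48 = 89.6% | 43/43 v 43/43 (100% v 100%) | no test | no test |
| 43 | 3 | 43/48 = 89.6% | 43/43 v 43/46 (100% v 93.5%) | 0.24 | 0.088 |
| 38 | 6 | 38/48 = 79.2% | 38/38 v 38/44 (100% v 86.4%) | 0.028 | 0.018 |

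With x = 42, Fisher's p for k = 3, 4, 5 and 6 is 0.24, 0.12, 0.057 and 0.028, so about six late-converting controls are needed for significance.

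**4. How often the PP test would be falsely significant.** Fix the investigational arm at 100%. Let the control count be binomial with probability (rate by month 6)/(rate by month 8), and enumerate exactly at the two-sided 5% level, 48 per arm:

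| True rate by month 6, both arms | Control rate by month 8 | Expected control PP proportion | Fisher | Chi-square |
|---|---|---|---|---|
| 90% | 90% | 100% | 0% | 0% |
| 95% | 97% | 97.9% | 0.0% | 1.6% |
| 90% | 95% | 94.7% | 3.3% | 22.2% |
| 85% | 95% | 89.5% | 35.5% | 54.0% |
| 80% | 95% | 84.2% | 75.5% | 87.2% |

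The conversion rates in steps 3 and 4 are assumptions. The documents give none for months 6 or 8.

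**5. Tables 16 and 17.** Two-month conversion is not fixed by PP membership. With x = 38, k = 6 and an assumed 30 two-month converters per arm, mITT is 30/48 = 62.5% in both arms. PP is 30/38 = 78.9% v 30/44 = 68.2%, Fisher p = 0.32: shifted towards the investigational arm, but free to vary. In Table 16, every investigational PP conversion falls by month 6, while control conversions may fall later.

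**The case against.** Four points can be made against this.

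*The significant example is pessimistic.* Protocol 3.1 reports 88.3% and 90.5% conversion at three months in an earlier Korean MDR-TB trial. With 48 per arm that leaves 48 × 0.117 = 5.6 or 48 × 0.095 = 4.6 unconverted at month 3, and fewer at month 6. Six controls converting in months 6 to 8 would then be about all of them, or more. This stands as a limit on plausible size. It is not a proof, because the culture medium is not stated there and the patients and regimens may differ. It leaves the direction unchanged.

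*The 100% is inferred.* The PP definition does not name conversion, and the list of PP violations in SAP 3.1 does not name late conversion. Treatment failure in Protocol 6.4 requires termination or a permanent change of at least two drugs, so non-conversion alone does not trigger it. A late converter kept on treatment and labelled as 12-month could enter PP. That is true, but it would depart from the duration rule in Protocol 5.1.2 and would not make the comparison sound.

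*The medium is not named.* Protocol 5.2 specifies liquid culture for the primary outcome, and Protocol 5.1.2 names no medium for assigning duration. The strict 100% therefore holds for at most the row that governs duration. The other row shares the selection without the guarantee.

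*Little depends on it.* Secondary outcomes are described at an exploratory level (SAP 3.6.2) and PP is auxiliary (SAP section 5). This stands and limits the weight of the point.

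**Conclusion.** The concern holds for the PP comparison in Table 18. On the medium that governs duration (liquid, if Protocol 5.2 carries over), the investigational PP proportion is 100% when the protocol is followed, and the comparison cannot favour control. With equal true conversion the false-positive rate in the illustration runs from 0% to about 76% (Fisher) or 87% (chi-square). It depends on the control conversions in months 6 to 8. The three-month rates in Protocol 3.1 point to the lower part of that range.

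A reader might go further and infer that the PP p-values always favour the new regimen, or that all the PP conversion results are constants. The documents support neither. If no control converts in the window, both arms are at 100% and there is nothing to test. The solid row and the PP rows of Tables 16 and 17 are biased towards the investigational arm but not fixed. The mITT conversion results and the primary non-inferiority decision are unaffected.

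**What to change.** Base all between-arm tests of culture conversion on the mITT set.

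- Table 18: remove the PP comparison and its p-values, including those in the smear-positive and smear-negative sub-blocks.
- Tables 16 and 17: drop the PP p-values, or keep the PP rows as description only, with a footnote that investigational PP membership is conditional on conversion by month 6. The footnote should name the medium used to assign duration.
- SAP 5.2: add a sentence giving the reason.

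The cost is SAP wording and some table cells. No new data are needed, and the primary analysis and sample size do not change. The downside is the loss of a supportive exploratory display.
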